4.3. Data Cleaning

The data will then be checked to ensure that there are no erroneous entries and that all missing data is properly coded. Any changes will be made on the ACCESS database. After the database is cleaned and locked, it will be provided to the statistics team for analyses.

5. STATISTICAL ANALYSES

5.1. Primary Outcome Analysis

5.1.1. ITT analysis of the primary outcome - the primary analysis

The primary outcome is a binary composite outcome: occurrence of stillbirth, fetal, or birth defects identified from the 12 gestational weeks until 28 days after birth and will be summarised using number (%) of subjects with an event by treatment group.

The primary outcome will be analysed using a generalised estimating equation (GEE) model with treatment as the independent variable and center as the cluster effect. Binomial distribution, log link function and exchangeable working correlation matrix will be used in the GEE model, from which the treatment effect will be estimated as the risk ratio between the experimental arm and the control arm together with 95% confidence interval (CI). Main conclusion will be drawn from the GEE model based on ITT population.

In case the above GEE model does not converge, the following models will be fitted sequentially until convergence is achieved:

- GEE model with Poisson distribution;
- GEE model with Negative Binomial distribution;
- GEE model with Binomial distribution, logit link function and exchangeable working correlation matrix, from which odds ratio will be converted into risk ratio using the mathematical relationship between OR and RR as suggested by Localio, Margolis, and Berlin (2007).

In addition, GEE model with Binomial distribution, identity link function and exchangeable working correlation matrix will be used to calculate the risk difference between the experimental arm and the control arm together with 95% CIs. If the model does not converge, GEE model with Poisson distribution and Negative Binomial distribution will be subsequently fitted.

The above analysis will be implemented using SAS PROC GENMOD.

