3.4. Randomization and Blind

Randomization will be performed based on recruited clusters. Stata 15 was used for randomisation code generation. Twenty-two community health care centres (clusters) will be allocated to an experimental arm or a control arm with 1:1 ratio using permuted block randomisation method with block size of 4. Randomisation list will be generated by an independent statistician.

The study is single blinded, the participants from the either arm will not know the medical care provided by the opposite arm. The study investigators who are involved in recruitment, the laboratory staff, and the dose-adjusting investigator (who was not involved in participant care) will remain blinded, since all the study outcomes will occur and observed at maternity hospitals. The investigator involved in intervention

and the statistician was not blinded, as unbinding was required to carry out statistical procedures.

The fetus and birth defects observers were maternity hospital ultrasound department and neonatologists and do their work according to the usual protocol and the data of outcomes were retrieved from the medical records. Therefore, all outcome assessments will be masked. The trial statistician will also be blinded regarding the treatment code when he develops the statistical analysis plan and writes the statistical programmers, which will be validated and completed using dummy randomisation codes. The actual allocation will only be provided to the study team after lock of the database.

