3.5. Sample Size

Sample size calculation was performed based on the primary outcome- the incidence of a composite rate of fetus, still birth, or birth defects. The proportion of primary endpoint was conservatively estimated to be 8% in the control arm according to two recent observational studies^{6,7} and 4% in the experimental arm (or 50% reduction) based on the findings of a meta-analysis of randomized intervention trials of folic acid supplementation intervention in folate-deficient population⁸. With cluster size of 100 subjects per centre, K coefficient of 0.23, a power of 85 % and a 5 % level of type I error, 22 clusters (2200 patients or 1100 in each arm) will be required. To allow for a 10 % dropout rate, at least 111 subjects (2446 patients or 1223 in each arm) will be recruited in each centre.

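### The primary GEE on 22 centres fixes no small-sample variance correction and no t reference; an uncorrected sandwich with z limits would run at about 7.5% type I error, not 5%

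*SAP*

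**What the plan says.** Section 5.1.1 specifies a binomial, log-link, exchangeable GEE "model with treatment as the independent variable and center as the cluster effect", reported as a risk ratio with 95% CI. It gives this analysis the deciding role: "Main conclusion will be drawn from the GEE model based on ITT population". On software it says: "The above analysis will be implemented using SAS PROC GENMOD".

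The section also sets a sequence of fallback models for non-convergence, and an identity-link GEE that "will be used to calculate the risk difference between the experimental arm and the control arm together with 95% CIs". Section 5.2.1 reuses the strategy for the binary secondary outcomes.

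Section 3.5 sizes the trial with "K coefficient of 0.23, a power of 85 % and a 5 % level of type I error, 22 clusters". No section says which variance estimator, small-sample correction, reference distribution or degrees of freedom the GEE uses. Section 6 names STATA 15 for all analyses, with SAS and other packages as possible additions, so the software does not settle the question either.

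**The concern.** The sandwich variance is justified by a large number of clusters. With 11 per arm it is biased downward, because residuals around a fitted arm risk are smaller than deviations from the true risk. The z limit adds a second error, because it treats as known a variance that rests on about 20 degrees of freedom. Both errors narrow the interval.

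What is at stake is the interval and test that carry the trial's main conclusion. The choices left open change the CI width by 12-17% at equal centre sizes, enough to decide a borderline result. Distribution, link, working correlation and fallback order are all fixed, so the omission stands out. It is also an analysis detail that belongs in a SAP.

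**Working it through.** **Inputs.** From section 3.5: 8% v 4% event risk, 100 analysed per centre, K = 0.23, 22 clusters, 5% type I error, 85% power, 10% dropout. From section 3.4: 1:1 allocation, so 11 centres per arm if split evenly. Assumptions: K is the between-cluster coefficient of variation, the 5% is two-sided, and any size CV above zero is ours.

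**The plan's own figure.** Cluster formula per arm:

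c = a + (1.960 + 1.036)² × [p0(1-p0)/m + p1(1-p1)/m + k²(p0² + p1²)] / (p0 - p1)²

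- Bracket: 0.000736 + 0.000384 + 0.0529 × 0.0080 = 0.001543.
- Core term: 8.978 × 0.001543 / 0.0016 = 8.66.
- With a = 1 (unmatched): 9.66, so 10 per arm, 20 clusters.
- With a = 2 (the pair-matched variant): 10.66, so 11 per arm, which gives the stated 22.
- Dropout: 1100/0.9 = 1222.2, rounded up to 1223 per arm, 2446 in total.

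The 22 is reproduced, and it exceeds the unmatched requirement.

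**Analytic size, equal centres.** With 11 equal centres per arm, the uncorrected sandwich is 10/11 of the unbiased variance. Kauermann-Carroll restores the factor 11/10, and Mancl-DeRouen applies (11/10)². The t(20) limit is 2.086.

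| Variance and limit | Formula | Type I error |
|---|---|---|
| Uncorrected, z | 2P(t20 > 1.960 × √(10/11)) = 2P(t20 > 1.869) | 7.64% |
| Uncorrected, t(20) | 2P(t20 > 2.086 × √(10/11)) = 2P(t20 > 1.989) | 6.1% |
| Kauermann-Carroll, z | 2P(t20 > 1.960) | 6.4% |
| Kauermann-Carroll, t(20) | 2P(t20 > 2.086) | 5.0% |
| Mancl-DeRouen, t(20) | 2P(t20 > 2.086 × √(11/10)) = 2P(t20 > 2.188) | 4.1% |

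Both parts are needed: correcting only the variance, or only the limit, leaves about 6%.

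**Simulation** (beta-binomial centres, 11 v 11, mean size 100, k = 0.23, no true effect, 8% risk, exchangeable GEE):

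| Size CV (assumed) | Uncorrected, z | Kauermann-Carroll, t(20) | Mancl-DeRouen, t(20) |
|---|---|---|---|
| 0 | 7.6% | 5.0% | 4.0% |
| 0.2 | 7.7-7.8% | 5.1% | 4.1% |
| 0.4 | 8.2-8.6% | 5.3-5.6% | 4.3-4.4% |

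Ranges reflect two ways of handling a negative estimated correlation. At a common risk of 4% and equal sizes, the uncorrected figure is 7.5%. With k = 0 or a 12:10 split of centres it stays between 7.4% and 7.7%, so it does not hinge on how K is read. The risk-difference interval behaves the same way (7.6% at equal sizes, 8.2-8.6% at CV 0.4).

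**Under the planned effect (8% v 4%, equal sizes).**

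| Method | Coverage of the risk ratio | Power |
|---|---|---|
| Uncorrected, z | about 92.4% | 94% |
| Kauermann-Carroll, t(20) | 95.0% | 91% |
| Mancl-DeRouen, t(20) | 95.9% | 89% |

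CI width relative to uncorrected with z: √1.1 × 2.086/1.960 = 1.12 for Kauermann-Carroll, and 1.1 × 2.086/1.960 = 1.17 for Mancl-DeRouen.

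**The case against.** The SAP does not say that the sandwich will be uncorrected or that z limits will be used. A reader might infer that the trial will in fact be tested at 7.5%. The document does not support that: the figure belongs to one implementation of an unstated step. Uncorrected with t(20) gives about 6%. A model-based variance with z gives 5.5-6.6% if negative correlations are set to zero, and 7.3-7.5% if they are not. This part of the objection stands. What is certain is the omission, and that every uncorrected sandwich reading is above 5%.

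A reader might also infer from "at least 111 subjects (2446 patients or 1223 in each arm) will be recruited in each centre" that centres will be near equal, so the equal-size figure is the answer. That does not follow. The 111 is a minimum at recruitment, and section 4.1 then keeps only women who become pregnant and have a known primary outcome. Dropout alone would give a size CV of about √(0.1/(0.9 × 111.2)) = 0.03, but that ignores the conception step. The SAP gives no realised CV, so the rows above zero illustrate the direction and do not predict its size.

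Two further extensions are tempting. One is that the last fallback, "from which odds ratio will be converted into risk ratio using the mathematical relationship between OR and RR", lacks an interval rule. The SAP delegates that step to a cited method which cannot be checked here, so no claim is made. The other is that the same inflation applies to the continuous, IPTW, subgroup and count models. They were not simulated, so no size is claimed for them.

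On importance: with equal sizes, the correction changes significance only when the uncorrected p lies between about 0.029 and 0.05. That is 2.7% of null trials and 3.2% of trials at 8% v 4%. The point estimate does not move. This limits how often the choice matters, but those are the borderline results in which an open choice of variance does harm.

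**Conclusion.** The concern holds as a specification gap with a quantified consequence. The analysis carrying the main conclusion leaves open the variance correction and the reference distribution that 22 clusters require. At equal centre sizes, the uncorrected sandwich readings give a type I error between about 6% (t on 20 df) and 7.6% (z limits), against the 5% on which section 3.5 sizes the trial. Coverage with z limits is about 92.4%. Inequality in centre size adds to this.

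The figures rest on 11 centres per arm, mean analysed size 100, beta-binomial variation with K read as a coefficient of variation, and assumed size CVs. They cover the treatment-only binary models only.

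**What to change.** In section 5.1.1, state that the CI and p-value of the primary GEE use a Kauermann-Carroll bias-corrected sandwich variance with a t reference on 22 - 2 = 20 df. Report Mancl-DeRouen with t(20) as a sensitivity analysis, since Kauermann-Carroll drifts slightly above 5% when centre sizes vary. Apply the same rule to the risk difference, the fallback models and the binary secondary outcomes in section 5.2.1.

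Make the change before database lock and without sight of outcome by arm. Lock alone is not a sufficient safeguard. Section 3.4 says "The actual allocation will only be provided to the study team after lock of the database", but it describes the statistician as not blinded in one place and as blinded while writing the SAP and programs in another.

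Reconcile section 5.1.1 (SAS PROC GENMOD) with section 6 (STATA for all analyses), and confirm that the chosen package runs the correction.

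The cost is SAP wording and a software check, with no change to design or data. With equal sizes the primary CI is about 12% wider and power at 8% v 4% falls from about 94% to 91%. At an assumed size CV of 0.4, power falls from 93% to 90%. Both stay above the planned 85%.

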5.1.2. Sensitivity analyses of the primary outcome

- **PP analysis of the primary outcome**

The same analysis of the primary outcome will be performed in the PP population using a GEE model (described in 5.1.1).

- **Covariate adjusted analysis of the primary outcome**

A GEE model used for the analysis of the primary outcome in Section 5.1.1 will also be used for covariate adjusted analysis using inverse probability of treatment weighting (IPTW) approach. The covariates will include age (continuous variable), ethnic (binary variable), body mass index (continuous variable), adverse pregnant history (binary variable), parity (continuous variable), exposure to smoking (mother or father's smoking status, binary variable), total cholesterol (continuous variable), and RBC folate level (continuous variable) at baseline to estimate adjusted risk ratio and 95% CI. Covariate adjusted analysis will be performed on both ITT and PP populations.

We will first calculate a propensity score with treatment as the dependent variable (1 for the experimental group and 0 for the reference group), and all covariates listed above as independent variables through a logistic regression model with a random effect for the center, and then perform an IPTW analysis (weighted GEE model). The adjusted risk ratio between the two groups and its two-sided 95%CI will be estimated.

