3. STUDY DESIGN

3.1. Design

This is a definitive, single-blind cluster randomized controlled - superiority trial embedded within the primary care system to assess the real-world effectiveness of a package of tertiary interventions before and during gestation in reducing the incidence of fetus and birth defects compared with the standard usual perinatal care. We will

recruit prepare-for-pregnancy women and their husbands through the pre-pregnancy eugenics examination clinic. Blood samples will be collected for examining RBC folate concentrations at enrollment. According to the randomization plan, participants recruited from the same community health care centre (cluster) will receive the same intervention, and clusters allocated to the two arms will receive the standard care or a serious experimental care procedure. The methods and protocols for measuring the primary outcome and the secondary outcomes in the two arms will follow the same clinical routines.

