4. ANALYSIS POPULATIONS

4.1. Study Population Data Sets

Two study populations will be considered in the analysis as follows:

- **Intent-to-Treat (ITT) population**

ITT population will be defined as the pregnant women among preparing-for-pregnancy couples that were recruited since November 1, 2018, from the randomized clusters and finally get pregnant. Participants will be excluded from the ITT analysis if the primary outcome is missing, forming a modified ITT population (mITT).

- **Per protocol (PP) population**

PP population will only include participants who received the treatments according to the protocol. Specifically,

- Participants of the experimental group: will be considered non-compliant with the preconception intervention if their RBC folate levels do not reach the target level (400 ng/ml) at the 1st antenatal visit.
- Participants in the control group received the usual care only, no non-complaints will be defined.
- Participants in both groups who do not have RBC folate levels measured at the 1st antenatal visit will not be included in the PP population.

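### The propensity model has a centre random effect although every centre sits wholly in one arm, so the covariate-adjusted risk ratio is either the crude one or set by the software

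*SAP*

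**What the plan says.** Section 3.1 states that "participants recruited from the same community health care centre (cluster) will receive the same intervention", and section 3.4 that "Twenty-two community health care centres (clusters) will be allocated to an experimental arm or a control arm with 1:1 ratio".

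Section 5.1.2 plans a covariate-adjusted version of the primary analysis by inverse probability of treatment weighting. Treatment is the dependent variable of a propensity model with eight baseline covariates: age, ethnicity, BMI, adverse pregnancy history, parity, smoking exposure, total cholesterol and RBC folate. The score is obtained "through a logistic regression model with a random effect for the center, and then perform an IPTW analysis (weighted GEE model"). The section adds: "Covariate adjusted analysis will be performed on both ITT and PP populations".

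The fallback sequence for non-convergence in section 5.1.1 concerns the outcome GEE only. The same section states that "Main conclusion will be drawn from the GEE model based on ITT population".

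**The concern.** A random intercept for centre in a model for treatment makes sense when both treatments occur within centres. Here none has both. The centre effect separates the outcome of the propensity model perfectly, and the covariates are left to explain something the centre term already explains in full.

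The section also leaves open which score enters the weights: one that includes the predicted centre effect, one with the centre effect set to zero, or one averaged over its distribution. These behave very differently when the centre variance runs away.

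At stake is the only covariate-adjusted estimate of the primary outcome. It matters most in the per-protocol set. Section 4.1 treats experimental participants below the folate target at the first antenatal visit as non-compliant, but for controls says "Participants in the control group received the usual care only, no non-complaints will be defined". That selection works on one arm only, so comparability of the arms leans on the adjustment. A result labelled as adjusted that merely repeats the crude one would give false reassurance.

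**Working it through.** The plan gives no figure for this analysis, so there is none to reproduce. **Inputs from the SAP:** 22 centres allocated 1:1 (3.4), 100 per centre, 8% against 4% and K = 0.23 (3.5), one arm per centre (3.1). **Assumptions:** all covariate distributions, covariate intraclass correlations, imbalances and covariate effects used below.

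**1. Treatment is constant within centre in both populations.** This holds in ITT by design. Removing participants to form the per-protocol set cannot create variation within a centre.

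**2. The likelihood has no interior maximum.** Take 11 centres per arm, 100 participants each, centre effect σz with z standard normal. Without covariates the intercept is 0 by symmetry, and each centre contributes

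L(σ) = ∫ expit(σz)^100 φ(z) dz.

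As σ grows, expit(σz)^100 tends to 1 for z > 0 and to 0 for z < 0, so L(σ) tends to 0.5 and the log-likelihood to 22 × ln(0.5) = -15.249.

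| Centre SD | 1 | 5 | 20 | 100 | 500 | 5000 |
|---|---|---|---|---|---|---|
| Log-likelihood | -215.07 | -40.62 | -20.26 | -16.18 | -15.43 | -15.27 |

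It rises throughout. With 50 per centre the pattern is the same (-165.3 at SD 1, -15.27 at SD 5000). A 12:10 split is possible because 22 is not a multiple of the block size of 4; it only moves the ceiling, to 12 ln(12/22) + 10 ln(10/22) = -15.158. With eight simulated covariates (assumed intraclass correlation 0.03), the log-likelihood maximised over the coefficients rose in the same way in all three datasets: about -214 to -215 at SD 1, -64 at 3, -26.2 at 10, -18.5 at 30 and -16.1 at 100.

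**3. What happens to the weights.**

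- *Centre effect included.* Without covariates, the predicted effect b of a treated centre solves 100 × (1 - expit(b)) = b/σ². At σ = 1, b = 3.36, the score is 0.966 and the weight 1/0.966 = 1.035. At σ = 20, b = 8.46, the score is 0.9998 and the weight 1.0002. Stabilising multiplies by about 0.5, and constants within an arm cancel. In the eight-covariate simulations 96.5% of the imbalance remained at SD 1 and 99.98% at SD 20.
- *Averaged over the centre effect.* Scores move towards 0.5 and weights towards 2 as the SD grows. In simulation 50–57% of the imbalance remained at SD 1, 72–77% at SD 3 and 90–92% at SD 10.
- *Centre effect set to zero.* Between about 35% and 49% of the imbalance remained, depending on the assumed intraclass correlation and centre size.

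**4. What happens to the risk ratio.** In three simulated datasets a prognostic covariate was shifted by 0.4 SD in the experimental arm, with a true conditional risk ratio of 0.5:

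| Estimate | Set 1 | Set 2 | Set 3 |
|---|---|---|---|
| Crude | 0.725 | 0.702 | 0.756 |
| Centre effect included, SD 30 | 0.725 | 0.702 | 0.756 |
| Averaged, SD 1 | 0.677 | 0.630 | 0.687 |
| Averaged, SD 3 | 0.698 | 0.663 | 0.717 |
| Averaged, SD 30 | 0.722 | 0.698 | 0.752 |
| Centre effect zero, SD 30 | 0.670 | 0.617 | 0.676 |
| Ordinary logistic propensity model | 0.625 | 0.546 | 0.619 |

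With chance imbalance only, the crude ratios were 0.494, 0.547 and 0.526. Scores including the centre effect returned the same three values at SD 30. The ordinary logistic model gave 0.480, 0.515 and 0.515, with a largest weight of about 2.9 to 3.7.

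**The case against.** The strongest reply is about consequence. This is a sensitivity analysis, and the conclusion rests on the unadjusted ITT model. In ITT only chance imbalance is expected, and there the ordinary logistic model moved the risk ratio by just 0.01 to 0.03. From the SAP's own inputs, the standard error of the log risk ratio is about √[(0.92/8 + 0.96/4 + 2 × 0.23²)/11] = 0.205. The 95% interval around 0.5 is then roughly 0.33 to 0.75, and a shift of that size is small beside it. This stands for ITT. It does not carry over to the per-protocol set, where selection acts on one arm.

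Second, the absence of a finite estimate is exact for maximum likelihood only. A penalised, quasi-likelihood or Bayesian fit, or an optimiser that stops early, will return a number, and averaged scores at a small SD do adjust in part. That is correct, but the amount of adjustment then comes from the algorithm. The SAP names no estimator or package for this model, and section 6 allows five packages.

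Third, the larger risk-ratio contrasts use an imposed 0.4 SD imbalance, which is not a typical chance imbalance. They illustrate the mechanism and are not a forecast.

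**Conclusion.** The point holds and should be fixed. As written, the propensity model has no finite maximum-likelihood centre variance. Scores that include the centre effect reproduce the crude risk ratio, and the other readings give partial adjustment that depends on choices the SAP does not make. No fallback covers a failure of this model.

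The runaway variance and the collapse of the weights to about 1 follow from the design alone. The size of the gap between crude and properly weighted risk ratios depends on assumptions: 0.01 to 0.03 under simulated chance imbalance, and 0.10 to 0.16 under the imposed 0.4 SD imbalance (0.725 - 0.625, 0.702 - 0.546, 0.756 - 0.619). The primary analysis is not affected.

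**What to change.** In section 5.1.2, remove the centre random effect from the propensity model. Fit an ordinary logistic regression of treatment on the eight listed baseline covariates, state whether the weights are stabilised and whether they are truncated, and keep centre solely as the cluster in the weighted GEE.

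An acceptable alternative is to replace the weighting with a GEE for the outcome that includes the listed covariates directly. This is a different analysis, so the SAP should name one of the two before unblinding.

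The cost is about one sentence. No new data are needed, and the primary GEE in section 5.1.1 stays as it is.

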6. GENERAL CONSIDERATIONS FOR DATA ANALYSES

STATA® (version 15.0) will be used to perform all data analyses and generate the majority of data displays. SAS or SPSS or S-Plus or R may also be used for some data analyses and generating statistical graphs.

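### Section 5.1.2 feeds individual IPTW weights into the exchangeable-correlation GEE of 5.1.1; depending on how the software places the weights, they may no longer act as IPTW weights

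*SAP*

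**What the plan says.** Section 5.1.1 defines the primary model: "Binomial distribution, log link function and exchangeable working correlation matrix will be used in the GEE model", with treatment as the only predictor and centre as the cluster. It adds that "The above analysis will be implemented using SAS PROC GENMOD".

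Section 5.1.2 carries this model over: "A GEE model used for the analysis of the primary outcome in Section 5.1.1 will also be used for covariate adjusted analysis". Propensity scores for eight baseline covariates are estimated "through a logistic regression model with a random effect for the center", and the analysts "then perform an IPTW analysis (weighted GEE model". The analysis is run in both the ITT and PP populations and is listed as a sensitivity analysis. Section 5.1.1 reserves the main conclusion for the GEE in the ITT population.

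Under section 3.1, "participants recruited from the same community health care centre (cluster) will receive the same intervention", so treatment does not vary within a centre.

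No sentence changes the working correlation for the weighted model or says where the weights enter. Software is not fully fixed either: section 6 says that Stata 15 "will be used to perform all data analyses and generate the majority of data displays" and allows SAS and other packages for some analyses.

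**The concern.** IPTW balances covariates between arms because each woman counts in proportion to her weight. An independence working correlation preserves that. An exchangeable matrix may not: if the weights are treated as inverse variances inside the working covariance, the correlation term mixes each woman's weight with those of the others in her centre. Her contribution is then no longer proportional to her IPTW weight.

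This is the only covariate-adjusted analysis of the primary outcome. Its purpose is to show whether the unadjusted result survives adjustment, and a bias whose size and direction depend on an estimated ICC weakens that comparison. It could matter more in the PP population. Section 4.1 counts women below 400 ng/mL at the first antenatal visit as non-compliant in the experimental arm only, so baseline RBC folate, one of the eight covariates, may differ between the arms by more than chance.

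**Working it through.** **Inputs.** Section 3.5: risks of 8% and 4%, "With cluster size of 100 subjects per centre, K coefficient of 0.23", 22 centres, 85% power, 5% type I error (taken as two-sided), 10% dropout. Section 3.1: treatment constant within centre. Section 5.1.1: treatment-only GEE, exchangeable correlation.

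**1. The plan's own figure.** The SAP gives no number for the weighted model; its sample size supplies the ICC, so that was reproduced first. Clusters per arm = 1 + (q_α + q_β)² × [p0(1−p0)/m + p1(1−p1)/m + K²(p0² + p1²)] / (p0 − p1)². The bracket is 0.000736 + 0.000384 + 0.000423 = 0.001543; divided by 0.0016 it is 0.9645. Normal quantiles give 9.66. t quantiles on 20 df give 10.57, hence 11 per arm and 22 centres, as stated. Dropout: 1100/0.9 = 1222.2, hence 1223 per arm and 2446 in total, as stated. K = 0.23 is therefore the between-centre coefficient of variation.

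**2. Implied ICC = K²p/(1−p).** At 8%: 0.0529 × 0.08/0.92 = 0.0046. At 4%: 0.0529 × 0.04/0.96 = 0.0022.

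**3. Effective weight, with weights inside the working covariance (assumption).** Take V = A^½ W^−½ R W^−½ A^½. The fitted mean is constant within a centre, so woman j enters the estimating equation with weight proportional to w_j − c × mean(√w) × √w_j, where c = nρ/(1 + (n−1)ρ). This is w_j only if ρ = 0. For small deviations in the weights, the amplification is (1 − c/2)/(1 − c). At ρ = 0.0046: c = 0.46/1.4554 = 0.316, and 0.842/0.684 = 1.23.

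**4. Balance with a plain logistic propensity model (no centre effect).** Two simulations of 22 centres of 100, with one covariate, gave the residual imbalance as a share of the starting imbalance. Run A used a risk ratio of 1.5 per SD.

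| ICC | c | Amplification | Exchangeable, run A | Exchangeable, run B | Independence |
|---|---|---|---|---|---|
| 0.0022 | 0.18 | 1.11 | – | −11% | 0% |
| 0.0046 | 0.32 | 1.23 | −21% | −22% | 0% |
| 0.01 | 0.50 | 1.51 | −46% | −49% | 0% |
| 0.02 | 0.67 | 2.02 | −93% | −98% | 0% |
| −0.003 | −0.43 | 0.85 | – | – | – |

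A third simulation at K = 0.23 estimated the ICC in each trial. Mean standardised differences of 0.096, 0.294 and 0.477 became −0.021, −0.064 and −0.116, that is, 22%, 22% and 24% with reversed sign. Independence gave 0.000. The estimated ICC was negative in 14–18% of trials; amplification is then below 1 and the distortion runs the other way. With the weights multiplying the residuals outside R^−1, exchangeable correlation also gave 0.000.

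**5. Effect on the risk ratio.** Assume a 0.13 SD imbalance and risk ratio 1.5 per SD (log 0.405). The shift is 0.405 × 0.13 × 0.21 = 0.011, about 1%, at ICC 0.0046, and 0.405 × 0.13 × 0.93 = 0.049, about 5%, at ICC 0.02. In the third simulation (log risk ratio 0.4 per SD, true treatment risk ratio 1), the median exchangeable and independence estimates at K = 0.23 were 0.994 and 1.003, 0.966 and 0.992, and 0.959 and 1.010 for starting imbalances of about 0.1, 0.3 and 0.5 SD. Their ratios are 0.991, 0.974 and 0.950.

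**6. Yardstick.** The variance of the log risk ratio under the design inputs is 0.92/88 + 0.96/44 + 2 × 0.0529/11 = 0.0105 + 0.0218 + 0.0096 = 0.0419, so the standard error is about 0.20. A 1% shift is about one twentieth of that.

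**7. The propensity model as written.** Treatment is fixed by centre, so the random-centre likelihood keeps rising with the random-effect SD (log-likelihood −453 at SD 0.5, −17 at SD 50) and has no finite estimate. With predicted centre effects at SD 5, the weights run only from 1.0014 to 1.0039, and an imbalance of 0.299 stays at 0.298 under exchangeable correlation at ICC 0.0046. Using only the fixed part (SD held at 5), 0.299 becomes 0.143 under independence and 0.108 under exchangeable correlation: under-correction, with no sign change.

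**The case against.** The strongest objection is that the plan as written does not over-correct. A reader might infer from the pairing of IPTW weights with an exchangeable matrix that the adjusted risk ratio will overshoot and leave the covariates unbalanced in the opposite direction. The documents do not support that. Three conditions are needed: weights inside the working covariance, a positive estimated ICC, and a propensity model that yields real weights. The SAP settles none of the three. It does not state the placement, its software wording leaves the implementation open, and its random-centre propensity model gives little or no adjustment. This part of the objection stands.

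It also stands that the shift is small at the planned ICC, that the larger figures need ICCs two to four times the plan's, and that the simulations used one covariate with an assumed prognostic effect. The analysis does not carry the main conclusion. It would go too far to say that the adjusted result cannot be interpreted for this reason alone.

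The objection does not remove the point. Once the centre effect is dropped from the propensity model, the weights become real and this distortion can appear. Changing the working correlation alone is not enough either, since independence with the fixed part of the present propensity model still leaves 0.143 of 0.299.

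**Conclusion.** The concern holds in a conditional form. The plan combines individual IPTW weights with an exchangeable working correlation and does not say how the weights enter. With weights inside the covariance, a positive estimated ICC and a usable propensity model, the adjusted analysis can over-correct by about one fifth of the starting imbalance at the plan's ICC of 0.0046. The assumed ICCs of 0.01 and 0.02 give about 46% and 93%. The risk ratio shift at the planned ICC is about 1% for a 0.13 SD imbalance on one covariate, and about 5% for a 0.5 SD imbalance. As the propensity model now stands, too little adjustment is the larger fault. Severity is minor: the sensitivity analysis is affected in both populations, the main conclusion is not.

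**What to change.** Add to section 5.1.2 that the weighted GEE uses an independence working correlation matrix with centre-level robust variance, and that the exchangeable matrix of 5.1.1 applies to the unweighted models only. In the same revision, remove the centre effect from the propensity model; either change alone leaves the adjusted analysis unsound. Report weighted covariate balance by arm, so that a reader can see whether the weights did their work.

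Independence lets the IPTW weights act as intended under either weight placement, so the software question need not be settled first. The cost is a few lines of SAP text, one option in the outcome-model code, one term fewer in the propensity model and one balance table. The downside is a small loss of efficiency if centre sizes turn out very unequal.
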